1.2 Number of Digits to be Displayed

Term	Definition
Percentage (%)	Incidence of AE, etc. or ADR, etc.: Displayed to two decimal places by rounding Other: Displayed to one decimal place by rounding
Summary statistics (mean/standard deviation)	Mean: Displayed to one lower digit than raw data by rounding Standard deviation:

Term	Definition
	Displayed to two lower digits than raw data by rounding
P-value	P-value will be displayed to three decimal places by rounding down. P-value rounded down to less than 0.001 will be displayed as p<0.001.

1.3 Level of Significance

Two-sided 5%

1.4 Handling of Test/Measurement Data

Test/measurement data will be handled in accordance with the criteria described below (with 1 month as 30 days). If there are multiple pieces of data at the same specified time point, data on the test day closest to the specified day of assessment will be employed, and the latest data among different pieces of data on different days with the same deviation from the specified day of assessment will be employed. At the final assessment*, values measured on the day closest to the start date of treatment with Zacras + 375 days will be employed (including values measured during the off-treatment period). Values measured after the end day of treatment with Zacras will not be employed.

The number of days from the start day of treatment with Zacras is 1 day for the start day of treatment with Zacras and -1 day for the previous day.

* After 12 months of treatment with Zacras (or at discontinuation of treatment with Zacras)

Time point of test	Permissible range (number of days from the start day of treatment)	Specified day of assessment
At the start of treatment	-90 to -1	Start date of treatment
After 1 month of treatment	1 to 45	Start date of treatment + 30
After 2 months of treatment	46 to 75	Start date of treatment + 60
After 3 months of treatment	76 to 105	Start date of treatment + 90
After 4 months of treatment	106 to 135	Start date of treatment + 120
After 5 months of treatment	136 to 165	Start date of treatment + 150
After 6 months of treatment	166 to 195	Start date of treatment + 180
After 7 months of treatment	196 to 225	Start date of treatment + 210
After 8 months of treatment	226 to 255	Start date of treatment + 240
After 9 months of treatment	256 to 285	Start date of treatment + 270
After 10 months of treatment	286 to 315	Start date of treatment + 300
After 11 months of treatment	316 to 345	Start date of treatment + 330
After 12 months of treatment	346 to 375	Start date of treatment + 360

At the final assessment	1 to 375	Start date of treatment + 375
-------------------------	----------	----------------------------------

2.0 Disposition of Patients (Patient Composition Diagram)

(1) Patients included in tabulation/analysis

Patients enrolled in the specified drug-use survey

(2) Data tabulated/analyzed

The number of enrolled patients, number of medical institutions involved in patient registration, number of patients from whom the CRF is collected, number of patients from whom the CRF is not collected, number of finalized patients, number of non-finalized patients, number of patients included in safety evaluation, number of patients excluded from safety evaluation, number of patients included in efficacy evaluation, and number of patients excluded from efficacy evaluation will be tabulated.

For the number of medical institutions involved in patient registration, one medical institution with different departments should not be counted more than once.

For patients from whom the CRF is not collected, the number of patients by reason for failure to collect and the total number will be tabulated.

For patients excluded from safety evaluation and those excluded from efficacy evaluation, the number of patients by reason for exclusion and the total number will be tabulated.

Patients meeting any of the criteria listed below will be handled as described below regarding whether to employ them or not.

Criterion	Enrollment	Safety evaluation	Efficacy evaluation
Duplicate registration (the same patient) [posterior finding]	×	-	-
Wrong registration (not prescribed) [posterior finding]	×	-	-
Treatment before the contract period [posterior finding]	○	×	×
Registration after 15 days of treatment with Zacras [posterior finding]	○	×	×
No data on blood pressure before or after treatment with Zacras	○	○	×
Deviation from inclusion criteria	○	○	×
Deviation from exclusion criteria	○	○	×
Failure to confirm the intake of Zacras [during the patient enrollment period]	×	-	-
Failure to confirm the intake of Zacras [after the patient enrollment period]	○	×	×

Unavailability of follow-up CRF	○	○	○
---------------------------------	---	---	---

○: employed, ×: excluded or not employed

(3) Table/figure number

Figure 2.0-1, Table 2.0-1

3.0 Patient Demographics and Baseline Characteristics

(1) Patients included in tabulation/analysis

Patients included in safety evaluation

(2) Data tabulated/analyzed

For each variable, patients will be categorized as described below, and the number and proportion of patients will be tabulated.

Variable	Category
Sex	Male, female
Age	Summary statistics
	<65 years, ≥65 years
	<65 years, 65 to 74 years, ≥75 years
Duration of disease	<1 year, 1 to <3 years, 3 to <5 years, ≥5 years, unknown
Diagnostic category (at the start of treatment with Zacro)	Outpatient, inpatient
Predisposition to hypersensitivity	No, yes, unknown
Concurrent illness	No, yes
Disposition (multiple tabulation)	Diabetes, dyslipidemia, hyperuricemia, cardiac failure, coronary artery disease (myocardial infarction (including old myocardial infarction), angina, or other), atrial fibrillation, renal impairment (chronic kidney disease (CKD) [diabetic nephropathy, nephrosclerosis, or other] or other), hepatic impairment (hepatic steatosis, alcoholic hepatopathy, or other), cerebrovascular disorder
Medical history	No, yes, unknown
Body weight (kg)	Summary statistics
	<40, 40 to <50, 50 to <60, 60 to <70, ≥70, not measured
BMI (kg/m ²)	Summary statistics
	<18.5, 18.5 to <25.0, 25.0 to <30.0, ≥30.0, unknown
eGFR [at the start of treatment] (mL/min/1.73 m ²)	Summary statistics
	<15, 15 to <30, 30 to <45, 45 to <60, 60 to <90, ≥90, unknown
Smoking history	Never smoked, current smoker, past smoker, unknown
Drinking history (drink alcoholic beverage almost every day)	Yes, no, unknown

Presence or absence of breast-feeding (at the start of treatment with Zacro) [only females]	No, yes
---	---------

(3) Table/figure number

Table 3.0-1

4.0 Treatment Given

(1) Patients included in tabulation/analysis

Patients included in safety evaluation

(2) Data tabulated/analyzed

For each variable, patients will be categorized as described below, and the number and proportion of patients will be tabulated.

Variable	Category
Initial dose of Zacras	LD, HD
Presence or absence of change in daily dose of Zacras	No, yes
Disposition	LD → HD, HD → LD
Duration of treatment with Zacras	1 to 180 days, 181 to 360 days, ≥361 days
Presence or absence of discontinuation of treatment with Zacras	No, yes
Reason for discontinuation of treatment with Zacras	Successful achievement of treatment goal, AE, patient's failure to visit the hospital such as transfer to another hospital, insufficient efficacy, other
Treatment with antihypertensive other than Zacras (at the start of treatment with Zacras)	No, yes
Disposition (multiple tabulation)*	ACE inhibitor, ARB, diuretic (thiazide and thiazide analogue diuretic), Ca antagonist, direct renin inhibitor, aldosterone antagonist, potassium-sparing diuretic, fixed-dose combination: ARB + diuretic, fixed-dose combination: ARB + Ca antagonist, fixed-dose combination: calcium antagonist + statin, other
Antihypertensive other than Zacras: treatment with HCTZ (at the start of treatment with Zacras)	No, yes
Disposition	6.25 mg, 12.5 mg, other
Treatment with	No, yes

antihypertensive other than Zpras (during the survey period)	
Disposition (multiple tabulation)*	ACE inhibitor, ARB, diuretic (thiazide and thiazide analogue diuretic), Ca antagonist, direct renin inhibitor, aldosterone antagonist, potassium-sparing diuretic, fixed-dose combination: ARB + diuretic, fixed-dose combination: ARB + Ca antagonist, fixed-dose combination: calcium antagonist + statin, other
Antihypertensive other than Zpras: treatment with HCTZ (during the survey period)	No, yes
Disposition	6.25 mg, 12.5 mg, other
Treatment with antihypertensive other than Zpras (within 2 months before the start of treatment with Zpras)	No, yes
Disposition (multiple tabulation)*	ACE inhibitor, ARB, diuretic (thiazide and thiazide analogue diuretic), Ca antagonist, direct renin inhibitor, aldosterone antagonist, potassium-sparing diuretic, fixed-dose combination: ARB + diuretic, fixed-dose combination: ARB + Ca antagonist, fixed-dose combination: calcium antagonist + statin, other
Number of concomitant drugs (antihypertensive other than Zpras)	
(at the start of treatment with Zpras)	0, 1, 2, 3, 4, 5, ≥ 6
(at the end of treatment with Zpras)	0, 1, 2, 3, 4, 5, ≥ 6
Concomitant non-antihypertensive drug (during the survey period)	No, yes

Disposition (multiple tabulation)	Antidiabetic, antidyslipidemic, antihyperuricemic, other
---	--

* For fixed-dose combinations, individual ingredients will be tabulated separately. If “fixed-dose combination: ARB + diuretic” is used concomitantly, for instance, “ARB” and “diuretic” will also be tabulated.

(3) Table/figure number

Table 4.0-1

5.0 Tabulation/Analysis of Safety

5.1 Occurrence of Adverse Events/Infections and Adverse Drug Reactions/Infections

5.1.1 Occurrence of Adverse Events/Infections

(1) Patients included in tabulation/analysis

Patients included in safety evaluation

(2) Data tabulated/analyzed

The following variables will be tabulated:

Variable	Data tabulated/analyzed
Number of patients with an AE, etc.	Number of patients who experienced an AE, etc.
Number of AE, etc.	Number of reported AE, etc. Multiple episodes of the same AE, etc. (PT) in the same patient will be tabulated as the total number of episodes.
Incidence of AE, etc.	The incidence of AE, etc. will be calculated as number of patients with an AE, etc./number of patients included in safety evaluation × 100.
Type of AE, etc.	AEs, etc. will be classified by SOC and then tabulated by PT. For laboratory tests, AEs, etc. will be classified by SOC, then sorted by HLGT, and finally tabulated by PT. For SOC, the number of patients with an AE, etc. and the incidence of AE, etc. will be listed by SOC internationally agreed order. For PT, the number and incidence of AE, etc. will be listed in ascending order of PT code. Multiple episodes of the same AE, etc. (PT) in the same patient will be tabulated as 1 patient/1 event.

(3) Table/figure number

Table 5.1-1

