4.0 Survey Population

The survey population consists of hypertensive patients who do not meet any of the exclusion criteria listed in Section 4.1. Refer to the “Precautions for Indication” (presented below) and “Precautions” sections in the package insert.

<Precautions for Indication>

Zacras Combination Tablets should not be used as the first-line treatment of hypertension. An excessive drop in blood pressure may occur.

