10.4 Matters on Safety

For the safety analysis set, data will be tabulated as described below. AEs will be coded according to the MedDRA/J and summarized using preferred term (PT) and system organ class (SOC).

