Patient with concurrent cardiac failure	Patient with a check for cardiac failure in the column of concurrent illness in the CRF or concurrent illness corresponding to SMQ code 20000004 (cardiac failure SMQ [scope: narrow]) described in the column of other disease: name of disease
Patient with concurrent coronary artery disease	Patient with a check for myocardial infarction or angina in the column of concurrent illness in the CRF, concurrent illness corresponding to SMQ code 20000043 (ischaemic heart disease SMQ [scope: narrow]) described in the column of other disease: name of disease, or PT corresponding to SMQ code 20000047 (myocardial infarction SMQ [scope: narrow]) described in the column of medical history
Patient with concurrent myocardial infarction (including old myocardial infarction)	Patient with a check for myocardial infarction in the column of concurrent illness in the CRF or PT corresponding to SMQ code 20000047 (myocardial infarction SMQ [scope: narrow]) described in the column of other disease: name of disease or medical history
Patient with concurrent angina	Patient with a check for angina in the column of concurrent illness in the CRF or concurrent illness corresponding to MedDRA PT code 10002383 (angina pectoris), 10002388 (angina unstable), 10036759 (Prinzmetal angina), or 10058144 (postinfarction angina) described in the column of other disease: name of disease
Patient with concurrent coronary artery disease (other)	Patient with concurrent coronary artery disease who is not a patient with concurrent myocardial infarction (including old myocardial infarction) or angina
Patient with concurrent atrial fibrillation	Patient with a check for atrial fibrillation in the column of concurrent illness in the CRF or concurrent illness corresponding to MedDRA PT code 10003658 (atrial fibrillation) described in the column of other disease: name of disease
Patient with concurrent renal impairment	Patient with a check for chronic kidney disease (CKD), diabetic nephropathy, nephrosclerosis, or other in the column of concurrent illness in the CRF or concurrent illness corresponding to the following (1), (2), or (3) described in the column of other disease: name of disease: (1) SMQ code 20000213 (chronic kidney disease SMQ [scope: narrow]) (2) Takeda MedDRA query (hereinafter referred to as TMQ) (Renal Disease) (3) TMQ (Renal Impairment)

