Patient with concurrent chronic kidney disease	Patient with a check for chronic kidney disease (CKD), diabetic nephropathy, nephrosclerosis, or other in the column of concurrent illness in the CRF or

Term	Definition
(CKD)	concurrent illness corresponding to SMQ code 20000213 (chronic kidney disease SMQ [scope: narrow]) described in the column of other disease: name of disease
Patient with concurrent diabetic nephropathy	Patient with a check for diabetic nephropathy in the column of concurrent illness in the CRF or concurrent illness corresponding to MedDRA PT code 10061835 (diabetic nephropathy) described in the column of other disease: name of disease
Patient with concurrent nephrosclerosis	Patient with a check for nephrosclerosis in the column of concurrent illness in the CRF or concurrent illness corresponding to MedDRA PT code 10029159 (nephrosclerosis) described in the column of other disease: name of disease
Patient with concurrent chronic kidney disease (CKD) (other)	Patient with concurrent chronic kidney disease (CKD) who is not a patient with concurrent diabetic nephropathy or nephrosclerosis
Patient with concurrent renal impairment (other)	Patient with concurrent renal impairment who is not a patient with concurrent chronic kidney disease (CKD), diabetic nephropathy, nephrosclerosis, or chronic kidney disease (CKD) (other)
Patient with concurrent hepatic impairment	Patient with a check for hepatic steatosis or alcoholic hepatopathy in the column of concurrent illness in the CRF or concurrent illness corresponding to the following (1), (2), or (3) described in the column of other disease: name of disease: (1) SMQ code 20000005 (hepatic disorders SMQ [scope: narrow]) (2) MedDRA PT code 10019708 (hepatic steatosis) MedDRA PT code 10001627 (alcoholic liver disease)
Patient with concurrent hepatic steatosis	Patient with a check for hepatic steatosis in the column of concurrent illness in the CRF or concurrent illness corresponding to MedDRA PT code 10019708 (hepatic steatosis) described in the column of other disease: name of disease
Patient with concurrent alcoholic hepatopathy	Patient with a check for alcoholic hepatopathy in the column of concurrent illness in the CRF or concurrent illness corresponding to MedDRA PT code 10001627 (alcoholic liver disease) described in the column of other disease: name of disease

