5.0 Tabulation/Analysis of Safety

5.1 Occurrence of Adverse Events and Adverse Drug Reactions/Infections

5.1.1 Occurrence of Adverse Events

(1) Patients included in tabulation/analysis

Patients included in safety evaluation

(2) Data tabulated/analyzed

The following variables will be tabulated:

Variable	Data tabulated/analyzed
Number of patients with an AE	Number of patients who experienced an AE
Number of AE	Number of reported AE. Multiple episodes of the same AE (PT) in the same patient will be tabulated as the total number of episodes.
Incidence of AE	The incidence of AE will be calculated as number of patients with an AE/number of patients included in safety evaluation × 100.
Type of AE	AEs will be classified by SOC and then tabulated by PT. For laboratory tests, AEs will be classified by SOC, then sorted by HLGT, and finally tabulated by PT. For SOC, the number of patients with an AE and the incidence of AE will be listed by SOC internationally agreed order. For PT, the number of patients with an AE and the incidence of AE will be listed in ascending order of PT code. Multiple episodes of the same AE (PT) in the same patient will be tabulated as 1 patient.

(3) Table/figure number

Table 5.1-1

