5.3.2 Occurrence of Adverse Drug Reactions/Infections by Seriousness, Time of Onset, and Outcome

(1) Patients included in tabulation/analysis

Patients included in safety evaluation

(2) Data tabulated/analyzed

ADRs, etc. will be categorized for each variable as described below, and the type of ADR will be tabulated.

Variable	Category
Seriousness	Serious, non-serious
Time of onset	Days 1 to 180, Days 181 to 360, Day 361 or later
Outcome	Recovered, recovering, not recovered, recovered with sequelae, fatal, unknown

The type of ADR, etc. will be tabulated as described below.

Variable	Data tabulated/analyzed
Number of patients	Number of patients who experienced an ADR, etc. by SOC/PT
Number of ADR, etc.	Number of reported ADR, etc. by SOC/PT
Type of ADR, etc.	ADRs, etc. will be classified by SOC and then tabulated by PT. For laboratory tests, ADRs, etc. will be classified by SOC, then sorted by HLGT, and finally tabulated by PT. ADRs, etc. will be listed for SOC by SOC internationally agreed order and for PT in ascending order of PT code. Multiple episodes of the same ADR, etc. (PT) in the same patient will be tabulated by category as the total number of episodes (for instance, one episode of serious diarrhoea and one episode of non-serious diarrhoea in the same patient will be counted once in the respective categories).

(3) Table/figure number

Table 5.3-2

5.4 Incidence of Adverse Drug Reaction/Infection by Factors Related to Patient Demographics and Baseline Characteristics and Treatment Given

(1) Patients included in tabulation/analysis

Patients included in safety evaluation

(2) Data tabulated/analyzed

ADRs, etc. will be categorized for each variable as described below, and the incidence of ADR, etc. will be tabulated.

ADRs, etc. will be categorized for each variable as described below, and the type of ADR, etc. will be tabulated. The type of ADR, etc. will be tabulated as described in Section 5.1. For disposition of treatment with antihypertensive other than Zacras (at the start of treatment with Zacras) and disposition of treatment with antihypertensive other than Zacras (during the survey period), “other” will not be tabulated.

Variable	Category
Sex	Male, female
Age	<65 years, ≥65 years ----- <65 years, 65 to <75 years, ≥75 years
Predisposition to hypersensitivity	No, yes, unknown
Concurrent illness	No, yes

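### Safety tables count patients by preferred term, by SOC and overall, but never by a pre-specified group of terms, so a clinical event spread over several terms has no patient count in the small groups of interest

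*SAP*

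**What the plan says.** Protocol 10.4 sets the frame: "AEs will be coded according to the MedDRA/J and summarized using preferred term (PT) and system organ class (SOC". The SAP file holds three editions; the current one stands first.

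- **Earliest SAP edition, 5.1.1 (adverse events):** "AEs, etc. will be classified by SOC and then tabulated by PT".
- **Current SAP 5.1.1 (adverse events):** "AEs will be classified by SOC and then tabulated by PT". Section 5.1.2 does the same for adverse drug reactions (ADRs). Each SOC also has a number of patients and an incidence, and there is an overall count of patients with any event.
- **Removal of duplicates within a PT:** "Multiple episodes of the same AE (PT) in the same patient will be tabulated as 1 patient". No rule covers different PTs that describe one clinical event.
- **Intermediate level:** for laboratory tests the terms are sorted by HLGT, but no patient count is specified at that level.
- **Current SAP 5.4 (ADRs by factor, including age, renal and hepatic impairment):** "The type of ADR, etc. will be tabulated as described in Section 5.1". This section gives ADRs only, plus the overall ADR incidence for each factor.
- **SAP 1.1 (illness at the start):** here the plan does group terms. Concurrent angina is built from four PTs, "10002383 (angina pectoris), 10002388 (angina unstable), 10036759 (Prinzmetal angina), or 10058144 (postinfarction angina", and concurrent hepatic impairment uses "SMQ code 20000005 (hepatic disorders SMQ [scope: narrow" among other criteria. Renal impairment uses a chronic kidney disease SMQ and two sponsor queries (TMQs). None of these lists is applied to events on treatment.

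**The concern.** Protocol Table 1 lets an adverse event be a laboratory finding, a symptom or a disease. One organ problem can therefore be reported under a laboratory term in one patient and a clinical term in another, in different PT rows and possibly different SOCs. SAP 1.1 shows that the sponsor knows a single PT may not capture a condition, since it builds baseline illness from lists.

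Protocol 3.2 names renal impairment, hepatic impairment and age 75 or over as the populations with important missing information, and expects 70, 100 and 200 of them. In groups of that size, splitting an event over rows can leave each row with 0 or 1 patient. The reader of the final tables then cannot say how many renal patients had, for instance, a renal event of any kind.

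**Working it through.** **1. Is there a grouped count anywhere?** The plan states no figure to reproduce, so the first step is a reading of the current SAP's safety sections.

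| Section | Unit counted | Grouped terms for events on treatment? |
|---|---|---|
| 5.1, 5.2 | PT, SOC, overall | No |
| 5.3 (seriousness, onset, outcome) | SOC/PT | No |
| 5.4 (by factor) | overall ADR incidence, then the layout of 5.1; ADRs only | No |
| 5.5, 5.6 (serious events) | PT, SOC, overall | No; the sponsor's medically significant list only sets the seriousness flag |
| 5.7 (pulse, laboratory) | summary statistics | No; no abnormality thresholds |

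The blood pressure tables in section 6 use only upper cut-offs (<140 and <90 mmHg), so they do not count low readings.

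**2. Can the count be recovered from the PT rows?** Only as bounds: the number of distinct patients lies between the largest row and the sum of the rows. Two hypothetical cases, with exact (Clopper-Pearson) 95% intervals that the SAP does not itself plan:

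- Rows of 2, 1 and 1 in 70: from 2 patients (2/70 = 2.86%; 0.35 to 9.94) to 4 patients (4/70 = 5.71%; 1.58 to 13.99).
- Rows of 12, 9 and 6 in 1,000: from 12 patients (1.20%; 0.62 to 2.09) to 27 patients (2.70%; 1.79 to 3.90).

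**3. How much does splitting hide?** The documents give no event rate, so these inputs are assumptions: risk 3% for the clinical event, split evenly over three PTs (1% each), with at least 2 patients as a simple marker of a repeated event. Group sizes are from Protocol 3.2.

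Formula: P(X ≥ 2) = 1 − (1 − p)^n − n·p·(1 − p)^(n−1).

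- n = 70, grouped (p = 0.03): 1 − 0.1186 − 0.2567 = 0.625.
- n = 70, one PT (p = 0.01): 1 − 0.4948 − 0.3499 = 0.155.
- n = 70, at least one of the three PT rows, treating rows as independent: 1 − (1 − 0.155)^3 = 0.397.

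| n | Grouped | A given PT | At least one of three PTs |
|---|---|---|---|
| 70 | 62% | 16% | 40% |
| 100 | 81% | 26% | 60% |
| 200 | 98% | 60% | 93% |
| 1,000 | about 100% | about 100% | about 100% |

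**4. Sensitivity.** With the same even split over three PTs and n = 70, an assumed risk of 1% gives 16% grouped against 2% for a given PT; 5% gives 87% against 33%. If one PT carries 2 of the 3 percentage points, that PT alone reaches 1 − 0.2431 − 0.3473 = 41% at n = 70, so an uneven split shrinks the loss but does not remove it.

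**The case against.** Much of the case on the other side stands.

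- **Counts above PT level exist.** Each SOC row counts patients, and 5.4 gives overall ADR incidence for each factor. A reader might infer that organ-level events get no patient count at all; the SOC rows contradict that. They also tighten the bounds: rows of 2, 1 and 1 inside a SOC with 3 patients mean 2 or 3 patients, not 4. What remains is that a SOC row mixes in unrelated events and misses related terms filed under another SOC.
- **The SAP does what its protocol says.** Protocol 10.4 asks for PT and SOC, and no grouped event of interest is defined. A reader might infer a contradiction or a wrong figure; there is neither.
- **Low blood pressure is not a survey endpoint.** "An excessive drop in blood pressure may occur" in Protocol 4.0 is a package-insert precaution on first-line use. It makes a grouped row sensible but does not make its absence a breach of the plan.
- **The size is assumed.** Risk, number of PTs, even split and the threshold of 2 are not in the documents, which set no decision rule at 2 patients. No event disappears through splitting; it is only spread out.
- **Existing lists may not fit.** The SMQs and TMQs were named for concurrent illness, and their contents are not shown. A list for chronic disease need not cover acute events. Nothing in the documents ties the cardiac failure, ischaemic heart or cerebrovascular lists to a treatment risk, so there is no case for grouping those.
- **Grouping could be done later** from the coded data. That is true, but the choice of terms would then follow sight of the results.

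**Conclusion.** The point holds as an omission that is cheap to repair. The current SAP tabulates adverse events and ADRs by PT, SOC and overall (by factor, ADRs only), and no table counts each patient once for a clinical event whose terms span several PTs or SOCs. PT and SOC rows give bounds on that number, not the number itself.

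In the full 1,000 patients the loss is negligible at a risk of 3% or more. In the renal, hepatic and age 75 or over groups it can be material: under the assumed 3% risk and even three-way split, 62% against 16% for a given PT at n = 70, and 81% against 26% at n = 100. These figures show direction and rough scale only. How far a real event would split depends on reporting and coding, which the documents do not describe.

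**What to change.** In current SAP 5.1.1, 5.1.2 and 5.4, keep the SOC/PT rows and add three grouped rows, each counting a patient once:

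1. **Hepatic events:** the hepatic disorders SMQ already named in SAP 1.1.
2. **Renal events:** the renal TMQs already named in SAP 1.1, after a check that they cover acute events on treatment.
3. **Low-blood-pressure events:** one PT list, fixed before tabulation.

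Give the number of patients and the incidence overall and for renal impairment, hepatic impairment and age 75 or over. Because 5.4 covers ADRs only, adverse event counts for those three groups need their own rows; Protocol 10.4.2 already foresees adverse event incidence by such factors.

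The cost is a short SAP amendment, a medical decision on the term lists before tabulation, and a few extra rows. No new data are collected and no existing table changes.
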